### **Synopsis**

**Title:** Comparison of Pharmacodynamic Effects of Tirofiban vs. Cangrelor in NSTEMI Patients Undergoing Percutaneous Coronary Intervention

**Short Title:** Tirofiban vs. Cangrelor in NSTEMI

Rationale: Immediate potent inhibition of platelet function is critical for the prevention of periprocedural ischemic event occurrences in high risk N-ST segment elevation myocardial infraction (NSTEMI) patients undergoing percutaneous coronary intervention (PCI). Currently, dual antiplatelet therapy with aspirin and an oral P2Y12 receptor blocker (with loading doses) is widely used for PCI. However, immediate, potent and reversible inhibition of platelet aggregation is not possible even with the newer oral agents, prasugrel and ticagrelor. Therefore, an intravenously administered GPIIb/IIIa receptor inhibitor (tirofiban) or P2Y12 receptor blocker (cangrelor) with fast onset and offset of actions will provide more desired antiplatelet effects in the setting of PCI. Cangrelor provides effective inhibition of only ADP-mediated upstream platelet activation and aggregation pathways via selective inhibition of the P2Y12 receptor whereas a GPIIb/IIIa inhibitor such as tirofiban, will provide effective platelet inhibition by inhibiting the final common pathway of platelet aggregation stimulated by multiple agonists such as collagen, thrombin receptor activator peptide (TRAP), arachidonic acid (AA) and adenosine diphosphate (ADP). The latter may translate in to superior clinical benefits compared to cangrelor therapy. 2,3

## **Objectives:**

**Primary Objective:** Assessment of platelet aggregation in response to thrombin receptor activator peptide (TRAP) at baseline and serially following tirofiban or cangrelor infusion.

# **Secondary objectives:**

- 1) Assessment of platelet aggregation in response to ADP and collagen at baseline and serially following tirofiban or cangrelor infusion.
- 2) Assessment of ADP-induced and thrombin induced platelet-fibrin clot strength by thrombelastography (TEG6S)
- 3) Assessment of thrombin generation kinetics by Calibrated Automated Thrombogram (CAT).
- 4) Real time evaluation of shear-induced thrombus formation using novel RUO T-TAS® plus system.
- 5) Assessment of High sensitivity troponin and CK-MB.

**Study Type**: This is a single center open label, randomized, observational study.

[figure not shown]
Study Design: Prospective, single center, observational study. NSTEMI patients undergoing PCI: 30 patients each will be treated with tirofiban or cangrelor (total n=60). The study is modelled after CLEAR PLATELETS study.4

**Study Methodology**: This investigation will be conducted in NSTEMI patients undergoing PCI at IHVI Fairfax hospital. Platelet activation and aggregation, clot characteristics, thrombin generation kinetics, real time thrombus formation, and high sensitivity troponin/CK-MB will be assessed at the baseline, and 10 minutes, 30 minutes post-start of the infusion and 30 minutes, 1 hour, 2 hour, 4-6 hour and 12-24 hour following the end of infusion of tirofiban or cangrelor (study flow diagram).

Patients: Sixty patients with NSTEMI undergoing PCI.

**Statistical Methodology:** Sample size (n=60 patients) is based on the CLEAR PLATELETS study. Categorical variables will be compared using  $\chi^2$  test or the Fisher exact test as appropriate whereas continuous variables will be assessed using the Student unpaired t- or Mann-Whitney U test, and ANOVA test after checking for normal distribution. The pharmacodynamic effect of different regimens will be compared using a linear mixed model. Each model will include treatment, time, an interaction between treatment and time, and the baseline pharmacodynamic parameter as covariate. Analyses will be performed with SPSS software (SPSS, Inc., Chicago, IL) and p<0.05 will be considered significant.

# **Study Flow Diagram**

#### Time points

Baseline, 10 minutes, and 30 minutes post-start of the infusion, and 30 minutes, 1 hour, 2 hour, 4-6 hour and 12-24 hour following the end of infusion of tirofiban or cangrelor.

### **Laboratory Assays**

- 1) Platelet aggregation by LTA (5 and 20 uM ADP, 4 ug/ml collagen and 10 and 20 uM TRAP).
- 2) ADP- and thrombin-induced platelet-fibrin clot strength by TEG6S.
- 3) Thrombin generation kinetics by Calibrated Automated Thrombogram (CAT) at baseline and 10 minutes post-start of the infusion.
- 4) Annexin binding and p-selectin at (baseline,1 hr and 12-24 hr) by flow cytometry.
- 5) Real time evaluation shear-induced thrombus formation by novel RUO T-TAS® plus system.
- 6) High sensitivity troponin/CKMB at baseline, and 2, 4-6 and 12-24 hour after the end of the infusion

#### INTRODUCTION

## **Specific Aims**

To measure platelet activation and aggregation, clot characteristics, thrombin generation kinetics, real time thrombus formation at the baseline, and 10 minutes, 30 minutes post-start of the infusion and 30 minutes, 1 hour, 2 hour, 4-6 hour and 12-24 hour after the end of the infusion of tirofiban or cangrelor, and high sensitivity troponin and CK-MB at the baseline, 2 hour, 4-6 hour and 12-24 hour after the end of the infusion of tirofiban or cangrelor.

# 1) Platelet aggregation:

ADP-, collagen-, and TRAP -induced platelet aggregation by light transmittance aggregometry.

- 2) Platelet activation markers: P-selectin, and annexin binding by flow cytometry.
- 3) Platelet-fibrin clot characteristics and ADP-induced platelet-fibrin clot strength: Thrombin- and ADP-induced platelet-fibrin-clot strength, time to initial thrombin generation, and functional fibrinogen by thrombelastography (TEG6S).
- 4) Shear-induced platelet aggregation: Shear-induced platelet aggregation by T-TAS perfusion flow chamber using novel RUO T-TAS® plus system.
- 5) Thrombin generation kinetics: thrombin generation kinetics by Calibrated Automated Thrombogram (CAT).
- 6) High Sensitivity troponin and CK-MB

# 1.2 Hypothesis

Serial evaluation of pharmacodynamic effects of tirofiban vs. cangrelor using various established laboratory assays will distinguish the superior pharmacodynamic benefits of tirofiban vs. cangrelor.

### **Background and Significance**

It is estimated that, approximately 70% of the >780,000 persons with ACS in the United States, are diagnosed with NSTEMI. Based on the CRUSADE (Can Rapid risk stratification of Unstable angina patients Suppress ADverse outcomes with Early implementation of the ACC/AHA Guidelines) registry and ACTION Registry®-GWTG™ (Acute Coronary Treatment and Intervention Outcomes Network-Get With the Guidelines), 54-58% of NSTEMIs are managed with PCI. Usually NSTEMI patients are older patients with more comorbidities, more risk for recurrent ischemic events and more incidences of previous MI. Platelets play a critical role in periprocedural ischemic event occurrences including MI and stent thrombosis in patients with NSTEMI. Immediate potent inhibition of platelet function is critical for the prevention of periprocedural ischemic event occurrences in high risk N-ST segment elevation myocardial infraction (NSTEMI) patients undergoing percutaneous coronary intervention (PCI). Management of these patients during PCI with optimal antiplatelet therapy is crucial since these patients may require more effective antiplatelet therapy to overcome increased ischemic risk but bleeding risk is also high due to older age.

Currently, dual antiplatelet therapy with aspirin and an oral P2Y12 receptor blocker (with loading doses) are widely used for PCI. However, immediate, potent and reversible inhibition

of platelet aggregation is not possible even with the newer oral agents, prasugrel and ticagrelor. Therefore, an intravenously administered GPIIb/IIIa receptor inhibitor (tirofiban) or P2Y12 receptor blocker (cangrelor) with fast onset and offset of actions will provide more desired antiplatelet effects in the setting of PCI. Cangrelor is a parenterally administered adenosine triphosphate (ATP) analog with a short half-life (3–6min), with rapid onset/offset of action, and dose-dependent and predictable pharmacodynamic effects. Cangrelor provides effective inhibition of only ADP-mediated upstream platelet activation and aggregation pathways via selective inhibition of the P2Y12 receptor. In the CHAMPION-PHOENIX trial, 11,145 patients with stable coronary artery disease (CAD) or acute coronary syndrome (ACS) received a bolus and infusion of cangrelor or a loading dose of 600 mg or 300 mg of clopidogrel. Cangrelor therapy was associated with a significantly reduced primary endpoint occurrence of death, MI, IDR, or stent thrombosis at 48 hours [4.7 vs. 5.9 %, odds ratio =0.78, p=0.005). The primary safety end point of severe bleeding at 48 hours was similar between the treatment groups [0.16% vs. 0.11% odds ratio=1.50, p=0.44]. The rate of stent thrombosis was lower in the cangrelor group compared with clopidogrel group [0.8% vs. 1.4%, odds ratio = 0.62, p=0.01]. Furthermore, the benefits associated with cangrelor were consistent across the subgroups of stable angina (n=1991), NSTEMI (n=2810), and STEMI (n=6138) (interaction, p=0.98), and whether the patient received clopidogrel 300mg LD or 600 mg LD (interaction, p=0.61). GUSTO severe bleeding was similar between groups. 6 Based on the favorable outcome observed in the CHAMPION-PHOENIX trial, the Food and Drug Administration Cardiovascular and Renal Drugs Advisory Committee recommended the approval cangrelor as an adjunct to PCI for reducing the risk of periprocedural thrombotic events such as MI, stent thrombosis and IDR.

A GPIIb/IIIa inhibitor such as tirofiban, will provide effective platelet inhibition by inhibiting the final common pathway of platelet aggregation stimulated by multiple agonists such as collagen, TRAP, and ADP. The latter may translate in to superior clinical benefits compared to cangrelor therapy.

#### 2 STUDY DESIGN AND SUBJECT SELECTION

#### 2.1 Study Type

This is a single center open label, randomized, observational study.

#### 2.2 Setting

The study will be done at Inova Fairfax Hospital in an inpatient setting. Screening will take place at the emergency room (ER), coronary angiography preparation room, or coronary angiography suite. Study procedures after obtaining consent will occur at the emergency room and IHVI (coronary angiography suite, coronary angiography recovery room, intensive care coronary care unit, and coronary care step-down units).

### 2.3 Duration of Study

Subject participation will be until date of discharge.

------

## 2.4. Number of Subjects and Randomization procedure

Sixty patients with NSTEMI undergoing PCI will be randomized to receive 1:1 tirofiban or cangrelor. Allocation of study treatment will be performed via a web-based interactive randomization system, based on a computer-generated random sequence with a random block size.

### 2.5. Study Population

# 2.5.1. Population Characteristics

2.5.1.1. Gender and racial and ethnic origin of subjects

The study's intended population is inclusive of both genders (males and females), and all racial and ethnic groups and subgroups.

## 2.5.1.2. Age of Subjects

Subject enrollment will be comprised of subjects >18 years of age.

## 2.5.2 Vulnerable Population

Children, pregnant women, institutionalized persons, and persons with decisional incapacity will be not be enrolled in this study.

### 2.6. Recruitment

Recruitment will occur at the Inova Fairfax Hospital. The expected length of the recruitment period is 24 months. If the study conduct (e.g. recruitment rate; drop-out rate; data quality; protocol compliance) does not suggest a proper completion of the trial within the reasonable time frame as agreed upon, the recruitment period may be extended to reach the desired sample size.

#### 2.7. Inclusion Criteria

The study will include subjects with non-ST elevation myocardial infraction (NSTEMI). Subjects may be enrolled if they appropriately fulfill all inclusion criteria.

- 1. NSTEMI meeting the following criteria:
  - a) Patients 18 years of age or older with one or more of the following symptoms: -new ST-segment depression or transient elevation of at least 1 mm -elevations in troponin I, troponin T, or creatine kinase MB levels above ULN
  - b) Eligible for ticagrelor, cangrelor, aspirin, UFH, and GP IIb/IIIa inhibitor treatment.
  - c) Admitted at cardiac catheterization laboratory hospital or associated facility.
  - d) Competent mental condition to provide informed consent.

#### 2.8. Exclusion Criteria

Subjects will be excluded from study participation if any of the exclusion criteria is met.

- 1. Unstable angina with negative troponin, STEMI
- 2. Cardiogenic shock
- 3. Refractory ventricular arrhythmias
- 4. New York Heart Association class IV congestive heart failure
- 5. Cardiac arrest within 1 week of study entry

Page 6 of 17

- 6. History of hemorrhagic or ischemic stroke, TIA, sub-arachnoid hemorrhage or intracranial neoplasm, arteriovenous malformation, or aneurysm
- 7. Fibrinolytic therapy within 48 hours of study entry
- 8. Active pathological bleeding or history of bleeding diathesis
- 9. Severe hepatic insufficiency
- 10. Current peptic ulceration
- 11. Increased bleeding risk, per investigator judgment
- 12. Known anemia (hematocrit<25%)/thrombocytopenia (platelet count <  $100,000 \,\mathrm{mm}^3$ )
- 13. Surgery within 4 weeks before study entry or planned surgery within 2 months after study entry
- 14. Any P2Y12 receptor inhibitor or GP IIb/IIIa inhibitor within 7 days of study entry
- 15. Receiving warfarin or other coumadin derivatives or NOACs within the last 10 days with an INR >1.5 secs or planned use during the hospitalization period
- 16. Contraindication to the use of ticagrelor and/or aspirin
- 17. Receiving or will receive oral anticoagulation or other oral antiplatelet therapy (except aspirin) that cannot be safely discontinued within the next 3 months
- 18. Receiving daily NSAIDs or COX2 inhibitors that cannot be discontinued or anticipated to require >2 weeks of daily NSAIDs or COX2 inhibitors during study
- 19. Investigational drug in last 30 days or presently enrolled in drug/device study
- 20. Pregnant or lactating women
- 21. Women of childbearing potential (post-menopausal women can be enrolled if at least 1 year of amenorrhea or surgically sterile) on oral contraceptives or planning a pregnancy.
  - \*Women of child-bearing potential who are not taking oral contraceptives and are not planning on becoming pregnant may be enrolled in the study. Safety urine pregnancy test will be done prior to and after the drug infusion.
- 22. Condition associated with poor treatment compliance (e.g., alcoholism, mental illness, or drug dependence)
- 23. Inability to provide written informed consent and to understand the full meaning of the informed consent

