## 3.2 Medications/Therapies Prohibited During the Study

The medications/therapies prohibited during the study are warfarin, anticoagulant other than UFH, oral direct anticoagulants, P2Y12 receptor blockers other than ticagrelor or cangrelor, glycoprotein IIb/IIIa inhibitors other than tirofiban. Potential and enrolled subjects on or started on prohibited medications will be excluded or exited from the study.

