# 3.4.2 **Secondary Endpoints**

- Relative differences in 15 and 20  $\mu$ M TRAP- induced platelet aggregation by light transmittance aggregometry between cangrelor and tirofiban therapy at all post-infusion time points except stated above.
- Relative differences in ADP and collagen-induced platelet aggregation by light transmittance aggregometry between cangrelor and tirofiban therapy at all post-infusion time points.
- Relative differences in P-selectin, and annexin binding between cangrelor and tirofiban therapy at 1 h and 12-24h after the end of the infusion.
- Relative differences in thrombin- and ADP-induced platelet-fibrin-clot strength, time to initial thrombin generation, and functional fibrinogen between cangrelor and tirofiban therapy at all post-infusion time points.
- Relative differences in shear-induced platelet aggregation between cangrelor and tirofiban therapy at all post-infusion time points.
- Relative differences in time to peak thrombin generation, peak thrombin generation and total thrombin generation between cangrelor and tirofiban therapy at 10 minutes post-infusion time point.
- Relative differences in peak high sensitivity troponin and CK-MB between cangrelor and tirofiban therapy will be assessed at 2 hour, 4-6 hour and 12-24 hour post-infusion time points.

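### Exclusion 15 makes its 10-day NOAC look-back depend on INR >1.5, so a recently stopped NOAC user with a lower INR is not clearly excluded

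*Combined protocol and SAP*

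**What the plan says.** Section 2.8 opens by making each criterion sufficient on its own: "Subjects will be excluded from study participation if any of the exclusion criteria is met". Three places then deal with anticoagulants.

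- **Item 15** has two limbs. The first is recent use qualified by INR: "Receiving warfarin or other coumadin derivatives or NOACs within the last 10 days with an INR >1.5 secs". The second, joined by an or, is planned use in hospital, with no INR condition.
- **Item 17** has neither a look-back nor an INR condition: "Receiving or will receive oral anticoagulation or other oral antiplatelet therapy (except aspirin) that cannot be safely discontinued within the next 3 months".
- **Section 3.2** bars "warfarin, anticoagulant other than UFH, oral direct anticoagulants", with no INR threshold and no look-back. It applies at screening as well as after enrolment: "Potential and enrolled subjects on or started on prohibited medications will be excluded or exited from the study". The last sentence of Section 3.1 does the same for subjects whose own provider prescribed a drug that 3.2 bars.

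The outcomes that an anticoagulant could plausibly move are secondary or safety outcomes. Section 3.4.2 lists "Relative differences in time to peak thrombin generation, peak thrombin generation and total thrombin generation between cangrelor and tirofiban therapy at 10 minutes" and the TEG clot variables, and Section 3.4.5 follows bleeding on the BARC scale. The primary endpoint (Section 3.4.1) is aggregation induced by 20 uM TRAP, 30 minutes after the infusion starts.

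**The concern.** Item 15 names NOACs beside the vitamin K antagonists and puts both under one INR condition. INR is a ratio, so the printed unit of seconds is wrong. It is used to monitor vitamin K antagonists, so an INR of 1.5 or less does not show that a NOAC has cleared. That is general laboratory knowledge; the documents do not discuss how INR relates to NOAC level.

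The neighbouring look-backs carry no laboratory condition: item 7 (fibrinolytics, 48 hours) and item 14 (P2Y12 and GP IIb/IIIa inhibitors, 7 days) exclude on use alone. For a NOAC user at or below the threshold, item 15's 10-day window does nothing. The deciding INR is also not among the baseline procedures in Section 5.1.1.

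At stake are the interpretability of the CAT and TEG endpoints in patients who carry residual drug, and the bleeding exposure of those patients under heparin and an intravenous antiplatelet agent.

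**Working it through.** This is a question of wording, so the check applies the rules to four patients who used a NOAC or are due to.

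| Patient | Item 15 | Item 17 | Sections 3.1 and 3.2 | Result |
|---|---|---|---|---|
| Taking a NOAC at screening, any INR | If INR >1.5 or in-hospital use is planned | If it cannot be stopped | Met | Excluded |
| NOAC planned in hospital, any INR | Met (planned-use limb) | If it cannot be stopped | Met once started | Excluded |
| NOAC stopped within 10 days, INR >1.5 | Met | Not needed | Not needed | Excluded |
| NOAC stopped within 10 days, INR <=1.5, none planned, can safely be stopped | Not met | Not met | Unclear | Not clearly excluded |

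The fourth row is the gap. Section 3.2 speaks of subjects who are taking or are started on a barred drug, and this patient is neither. The sentence in 3.1 refers to drugs that were prescribed, which could cover the patient, but it limits them to drugs barred during the study. Beyond these, only item 11 (the investigator's view of bleeding risk) might apply.

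Non-UFH anticoagulants given before consent raise a similar question. Section 3.2 bars them, Section 2.8 has no look-back for parenteral ones, and Section 2.2 allows screening in the emergency room. The text does not say whether one earlier dose brings a patient under 3.2.

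**Size.** The sample size of 60 cannot be reproduced, because Section 4.1 gives no effect size, SD or power. The point does not depend on it. The documents also give no NOAC prevalence, so what follows is illustration only.

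*Chance imbalance.* If k of 60 patients carry residual drug, the chance that all fall in one arm of 30 is 2 x C(60-k, 30-k) / C(60, 30).

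- k = 2: 2 x (30 x 29)/(60 x 59) = 0.49
- k = 3: 2 x (30 x 29 x 28)/(60 x 59 x 58) = 0.24
- k = 6: 0.024

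With 3 versus 0, that arm's mean moves by 3/30 = 0.1 SD for each 1 SD of individual effect. The standard error of the difference is sqrt(2/30) = 0.258 SD, so the shift is 0.1/0.258 = 0.39 standard errors.

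*Noise.* At 30 per arm and two-sided 0.05 (the plan states 0.05 but not the sidedness), the difference detectable with 80% power is (1.96 + 0.84) x sqrt(2/30) = 0.72 SD. If a share f of patients is shifted by s SD, the variance is multiplied by 1 + f(1-f)s^2. Power at 0.72 SD, before any baseline adjustment, becomes:

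| Assumed f | Assumed s | Variance factor | Power |
|---|---|---|---|
| none | none | 1.00 | 80% |
| 2% | 1 SD | 1.02 | 79% |
| 5% | 2 SD | 1.19 | 73% |
| 10% | 2 SD | 1.36 | 67% |

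**The case against.** The strongest reply is that the plan already keeps out most of these patients. Planned in-hospital use excludes at any INR. Section 3.2 reaches potential subjects, so current NOAC users are out at any INR. The rules are cumulative: items 15 and 17 do not authorise entry of anyone whom 3.2 bars. All of this stands, and it narrows the point to recently stopped users. It does not close the gap, because neither 3.1 nor 3.2 clearly covers a drug already stopped.

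The consequence is also limited. Allocation is 1:1 and randomised (Section 2.4), and the baseline value is a covariate (Section 4.2). Section 3.1 gives UFH as needed, with different ACT targets in the two arms, so samples taken after the start may already reflect an anticoagulant given on purpose. This too stands, with two reservations. One baseline covariate does not fully describe a drug that is clearing while TEG is followed to 12-24 hours after the infusion, and no baseline adjustment applies to bleeding.

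Three stronger readings are tempting, and the documents do not support them.

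- *Recent NOAC users are excluded only when INR exceeds 1.5.* This ignores the planned-use limb and Section 3.2.
- *Two to six of the 60 would enter with residual drug.* This takes an assumed 3% to 10% of screened patients (0.03 x 60 = 1.8; 0.10 x 60 = 6) and applies it to enrolled ones. It also treats any use within 10 days as residual drug. Entry through the gap further requires that the drug was stopped, that none is planned, that items 6 and 17 do not apply and that the investigator sees no raised bleeding risk.
- *Item 17 excludes everyone, because all patients receive ticagrelor and only aspirin is excepted.* This needs the premise that ticagrelor cannot be safely stopped within 3 months, which the documents do not state. Inclusion 1b and exclusion 16 show that ticagrelor eligibility is intended.

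**Conclusion.** The concern holds in a narrow form. The recent-use limb of item 15 misfires for NOACs: a recently stopped user with INR <=1.5 and no planned in-hospital use is not caught by items 15 or 17, and not clearly by Sections 3.1 and 3.2. This is a stated rule that fails for a drug class it names, not a missing detail.

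The number of patients is unknown and probably small. The expected effect is noise or chance imbalance in the secondary CAT and TEG endpoints and a bleeding-safety concern. It is not systematic bias between arms, and nothing here shows an effect on the primary TRAP endpoint. Under the assumed scenarios the loss of power ranges from 1 to 13 percentage points (80% to 79%, or to 67%). The upper end needs 6 of 60 patients each shifted by 2 SD, with no help from baseline adjustment. The eligibility gap rests on the text alone; only its size rests on assumptions.

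**What to change.** Amend the wording in four places.

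1. Reconcile item 15 with Section 3.2, so that the INR condition attaches only to warfarin and coumadin derivatives and the protocol's own 10-day NOAC look-back operates without it. Keep the planned-use limb.
2. Delete the unit of seconds after the INR value.
3. State whether a non-UFH anticoagulant given before consent brings a patient under Section 3.2.
4. Reconcile the aspirin-only exception in item 17 with the ticagrelor listed in Section 3.1.

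The cost is a wording amendment and a few more screen failures. No new test or visit is needed.
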